2.6 Timing of Analysis

Primary endpoint and secondary endpoints analyses will be performed after subjects in the ITT analysis population reach their 6-month follow-up visits for endpoints analysis.

Statistical Analysis Plan

Final analysis will be performed after all randomized subjects completed 24 months follow-up visit or withdrew before their 24 months follow-up visit.

2.7 Study/Trial Success

The study will be considered as successful if the primary effectiveness endpoint is met, i.e., SCS is superior to CMM with regards to the responder rate.

2.8 Subgroups for Analysis

Primary endpoint will be analyzed by age (e.g., by median of the age or 65 cutoff depending on data distribution), diagnosis, and other subgroups which may help to understand outcomes for specific patient populations.

2.9 Handling of Missing Data

As discussed in Section 2.3.1.2, for a sensitivity analysis of the primary endpoint, subjects with missing primary endpoint outcomes will have their outcomes imputed with multiple imputation (MI). PROC MI in SAS will be used to multiply impute missing outcomes. Multivariate imputations by fully conditional specification (FCS) methods with 20 burn-in interactions before each imputation, and the number of imputations equal to the percentage of missing data, and a seed of 8684915 will be used for analysis. If FCS methods fail to converge, other methods will be explored for the MI model.

The model may include, but not be limited to, the following predictors:

- Randomization group
- Age
- Sex at birth
- Lower back NRS at baseline and 3 months
- Duration of pain

If the model does not converge with this list of predictors, predictors will be removed from the model as needed to ensure convergence.

Once multiply imputed datasets have been generated, each imputation will be analyzed with standard statistical analyses before being combined for inferential analyses using PROC MIANALYZE. Example code which may be used is included in Appendix B.

2.10 Poolability Issue

The poolability analysis of the primary endpoint will be conducted by the sites at 6 months. To evaluate the site effect on the primary effectiveness endpoint, interaction effect between treatment and sites on the primary effectiveness endpoint will be tested against an alpha level of 0.15 using logistic regression model. Only sites with a sufficient number of subjects will be included in this analysis. Sites must have at least 10 or more subjects to be included in the poolability analysis. If the poolability model does not converge, the number of subjects needed to be included in the analysis will be raised until the model converges.

Statistical Analysis Plan

If there is evidence of inconsistency of the responder rate across the sites, or if there is interaction observed between treatment and sites, subject's demographics, medical history and baseline characteristics may be examined.

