5.7 Number of Subjects

Approximately [REDACTED] subjects will be enrolled in the study. No site may contribute more than [REDACTED] % of the total sample. Assuming 25% attrition from randomization to 6 months in both groups, we expect approximately [REDACTED] evaluable subjects sufficient for the primary endpoint analysis ([REDACTED] %).

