APPENDIX XII: CIP SUMMARY

Clinical Investigation Name and Number	CRD_988 DISTINCT
Title	Dorsal spinal cord STImulatioN vs medi Cal management for the Treatment of low back pain
Objective(s)	The objective of this study is to evaluate the efficacy of BurstDR™ spinal cord stimulation, compared with conventional medical management, in improving pain and back pain-related physical function in patients suffering with chronic, refractory axial low back pain, who have not had lumbar spine surgery and for whom surgery is not an option.
Device Under Investigation	BurstDR™ capable products
Number of Subjects Required for Inclusion in Clinical Investigation	The study will enroll up to 270 patients at up to 30 US sites.
Clinical Investigation Design	This is a prospective, randomized, controlled, clinical trial
Primary Endpoint(s)	The primary effectiveness endpoint is the difference in responders between groups at 6 months. A subject is considered a responder for the primary endpoint if the following criteria are met: 
 • Improvement in pain, defined as a $\geq 50\%$ decrease on NRS
Subject Follow-up	• [REDACTED]
Inclusion Criteria	
 1. Patient must be willing and able to provide written informed consent prior to any clinical investigation-related procedure. 2. Age ≥ 18 years 3. Patient has chronic (at least 6 months), refractory axial low back pain with a neuropathic component and is not a candidate for spine surgery 4. Patient has back pain for ≥ 6 months inadequately responsive to supervised conservative care 5. Patient has not had spine surgery for back or leg pain 6. Patient is a candidate for spinal cord stimulation 7. Low back pain ≥ 6 on Numerical Rating Scale 8. Oswestry Disability Index score of $\geq 30\%$ Willing and able to comply with the instructions for use, operate the study device, and comply with this Clinical Investigation Plan

This confidential document is the property of Abbott and shall not be reproduced, distributed, disclosed or used without the express written consent of Abbott

Clinical Investigation Plan

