1.3 Clinical Investigation Design

This is a prospective, multi-center, randomized, controlled clinical trial with an optional crossover component. It is designed to evaluate the efficacy of BurstDR™ Spinal cord stimulation (SCS) in the treatment of chronic axial low back pain with a neuropathic component, compared with comprehensive medical management (CMM).

Subjects will be followed in-clinic for required study visits at 1,3, 6, 9, 12, 18 and 24 months and via phone call or optional clinic visit at 15- and 21-months. Due to the individualized nature of study therapies, patient reported outcomes will be continually assessed and additional patient outreach conducted in order to determine if therapy adjustment(s) are warranted to optimize pain control. The primary endpoint will be assessed at the 6-month follow-up visit. Upon completion of the 6-month follow-up visit, subjects who are dissatisfied with therapy and receiving inadequate improvement with their treatment assignment will be allowed to cross-over to the other treatment arm, if desired per Cross Over Instructions (CL1014686).

Up to 270 subjects will be randomized in the study which is split into two phases. Phase I will include the first minimal 200 randomized subjects. Phase II is the continued access phase and will include up to 70 randomized subjects.

Subject enrollment is expected to be completed within 18 months; subjects will be followed for 2 years. The total duration of the study is expected to be approximately 4 years, including enrollment, data collection from all subjects, and study close out.

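### The SAP's poolability rule raises its site-size cut-off until the model converges, with no minimum number of sites and no fallback, so the site-consistency test may rest on a few large sites or be impossible

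*SAP*

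**What the plan says.** SAP 2.10 assesses poolability of the primary endpoint across sites at 6 months. The treatment-by-site interaction "will be tested against an alpha level of 0.15 using logistic regression model". Entry is by size: "Sites must have at least 10 or more subjects to be included in the poolability analysis". The remedy for failure is conditional: "If the poolability model does not converge", then "the number of subjects needed to be included in the analysis will be raised until the model converges". If inconsistency or an interaction is found, "subject's demographics, medical history and baseline characteristics may be examined"; no other consequence is stated.

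The section does not say whether the 10 are randomised or evaluable subjects, whether site is a fixed or random effect, or what counts as non-convergence. It gives no upper limit for the cut-off, no minimum number of sites, no pooling of small sites and no alternative model.

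On size, the summary in Protocol Appendix XII says "The study will enroll up to 270 patients at up to 30 US sites", and SAP 1.3 says "Phase I will include the first minimal 200 randomized subjects". Protocol 5.7 caps each site's share ("No site may contribute more than"), but the percentage is redacted. The available text gives no expected site sizes.

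**The concern.** The entry threshold is high for the number of sites allowed, and the remedy for failure removes data. In a fixed-effect logistic model with a treatment-by-site interaction, the estimate for a site is infinite if either arm there has all responders or none. Small CMM groups with a 20% response rate will often have none. The cut-off must then rise past that site, and every other site of the same size or smaller goes with it. The retained set is thus chosen partly by outcome: a site with many SCS responders and no CMM responder is the kind of departure that a consistency check should see, and it is what triggers the removal.

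Randomisation is stratified by site (Protocol 6.3), but the primary Z-test does not use site (SAP 2.3.1.1). Section 2.10 is the only place where the SAP specifies a check of consistency across sites. At stake is whether that check has any content.

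**Working it through.** **Inputs from the documents.** 200 randomised in Phase I and up to 270 in all (SAP 1.3); up to 30 sites (Protocol Appendix XII); 3:2 allocation, response rates of 45% and 20%, 25% attrition (SAP 2.4); cut-off of 10 (SAP 2.10).

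**1. The plan's own figure from these inputs.** Evaluable subjects: 200 × 0.75 = 150, so 90 SCS and 60 CMM. SE = √(0.45×0.55/90 + 0.20×0.80/60) = 0.0736. Power = Φ(0.25/0.0736 − 1.96) = 92.5%. This agrees with the stated power of at least 90%. The SAP gives no figure for the poolability test itself.

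**2. Average site size.**

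| Sites | 200 randomised (evaluable) | 270 randomised (evaluable) |
|---|---|---|
| 15 | 13.3 (10.0) | 18.0 (13.5) |
| 20 | 10.0 (7.5) | 13.5 (10.1) |
| 30 | 6.7 (5.0) | 9.0 (6.75) |

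At 30 sites the average is below 10 even at full enrolment and before attrition.

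**3. Chance that a qualifying site is estimable.** A site with a SCS and c CMM evaluable subjects has both outcomes in both arms with probability (1 − 0.45^a − 0.55^a)(1 − 0.20^c − 0.80^c).

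- 6 SCS and 4 CMM: 0.964 × 0.589 = 0.568. The main cause of failure is no CMM responder: 0.80^4 = 0.41.
- Five such sites together: 0.568^5 = 0.06.
- 12 SCS and 8 CMM: 0.83.

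**4. Where the rule ends.** Assumptions: site is a fixed effect; non-convergence means that some retained site-by-arm cell has all or no responders; the count is of evaluable subjects; site sizes follow multinomial draws with gamma weights (shape 2, moderately uneven). The final cut-off is then one more than the size of the largest site with such a cell. The first four result columns use common response rates (5,000 trials per row). The last adds between-site variation in response with SD 0.3 on the logit scale.

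| Randomised, sites | Fails at 10 | Fewer than 2 sites left | 2 or fewer left | Evaluable subjects retained | Fewer than 2 left, site SD 0.3 |
|---|---|---|---|---|---|
| 200, 15 | 87% | 28% | 47% | 39% | about 30% |
| 200, 20 | 86% | 39% | 58% | 28% | 39% |
| 200, 30 | 78% | 54% | 74% | 16% | 56% |
| 270, 15 | 89% | 16% | 29% | 50% | 18% |
| 270, 20 | 93% | 25% | 40% | 36% | 25% |
| 270, 30 | 92% | 38% | 57% | 22% | 40% |

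**5. Sensitivity.** Thirty scenarios were run: 10 to 30 sites; equal, moderately uneven or very uneven sizes; 200 or 270 subjects.

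- Fewer than two sites remain in 6% (270 subjects, 10 very uneven sites) to 93% (200 subjects, 30 equal sites) of trials. This is the majority outcome in 8 of the 30 scenarios.
- Two or fewer sites remain in more than half of trials in 15 of the 30.
- With 200 subjects at 20 moderately uneven sites, an assumed CMM rate of 12%, 20% or 30% gives fewer than two sites in 66%, 39% or 18%.
- Applying the cut-off to randomised subjects moves the results by about three percentage points or less.

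**The case against.** The strongest objection is that the size of the problem rests on inputs the documents do not give. Thirty sites is a ceiling, Appendix XII pairs it with 270 rather than 200 subjects, site sizes are unknown, and the redacted cap limits how large a retained site can be. This stands. A reader might infer that the rule usually ends with too few sites to test anything. The documents do not support that: fewer than two sites is a minority outcome in 22 of the 30 scenarios.

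Second, the SAP does not say that the site effect is fixed or that non-convergence means an all-or-none cell. With a random site effect, or software that reports convergence despite sparse cells, the cut-off could stay at 10. A likelihood-ratio statistic can also still be computed when estimates diverge, although its calibration in such small cells is doubtful. This stands as a limit on the figures. It also shows that the section leaves the deciding terms undefined.

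Third, a reader might infer that the result will be presented as proof of consistency across sites, or that small sites are never examined. Neither document says the first. Against the second, 2.10 names inconsistency of the responder rate across sites as a separate trigger, though without a method.

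Finally, poolability does not gate the primary test (SAP 2.3.1.1), study success (2.7) or the secondary hierarchy (2.11). This stands in full and limits the weight of the point.

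**Conclusion.** The defect is in the text and does not depend on site sizes: the escalation has no stopping point short of convergence, no minimum number of sites and no fallback. Under a fixed-effect reading, the SAP's own rates make failure at the first cut-off likely: 59% to 99% of trials in 29 of the 30 scenarios. The exception is 200 subjects at 30 equal sites (32%), where few sites reach 10 at all. How far the rule then strips the analysis is uncertain: fewer than two sites in about 18% to 56% of trials for 15 to 30 moderately uneven sites, and 6% to 93% over the wider assumptions. The supportable conclusion is that the test may often rest on a few large sites or be impossible. No confirmatory conclusion changes. This is a minor point, held with medium confidence because site sizes, the cap and the meaning of non-convergence are not available.

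**What to change.** In SAP 2.10:

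1. Delete the provision that raises the cut-off until the model converges.
2. State that the count of 10 is of evaluable subjects, meaning those in the primary analysis of 2.3.1.1.
3. Keep all subjects by combining sites with fewer than 10 into pseudo-sites, under a rule fixed before outcomes are seen by arm (for example by region, then size).
4. State that site is a fixed effect in this model and define non-convergence. If the model still fails, fit a logistic mixed model with random site and treatment-by-site effects on all sites, and report the estimated between-site variance and the shrunken site-level effects.

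The cost is SAP wording and some programming; no data collection or design feature changes. The downsides should be acknowledged: power to detect an interaction stays modest, pooling can mask differences between small sites, and with few subjects per site the variance may be estimated as zero. The mixed model's behaviour at these site sizes was not simulated here and should be checked before it is adopted.

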2.11 Multiplicity Issues

To control for type I error inflation, the test of secondary endpoints will be performed in a hierarchical order at two-sided 5% significance level:

1. Secondary endpoint #1
2. Secondary endpoint #2
3. Secondary endpoint #3
4. Secondary endpoint #4
5. Secondary endpoint #5
6. Secondary endpoint #6
7. Secondary endpoint #7

The secondary endpoints will be tested only if the superiority in the SCS group is demonstrated in the primary endpoint. If hypothesis testing for superiority of secondary endpoint #1 fails, no hypothesis testing for the rest of secondary endpoints, etc.

2.12 Sensitivity Analysis

Sensitivity analysis will be conducted for the primary endpoint, as specified in Section 2.3.1.2.

3.0 DESCRIPTIVE ENDPOINTS AND ADDITIONAL DATA

3.1 Baseline and Demographic Characteristics

Baseline and demographic variables will be summarized based on the ITT and PTE analysis populations.

3.2 Adverse Events

All subjects who completed their enrollments will be included in the analyses. Serious adverse events (SAEs) and AEs, will be summarized using number of events, the percentage of subjects with events, and event rates by subject year for all subjects and by the relatedness (including COVID related) of events.

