5.4 Subject Enrollment

A patient is considered enrolled in the clinical investigation from the moment the patient provides written informed consent, has been confirmed to meet all inclusion criteria and none of the exclusion criteria, and eligibility has been confirmed by the medical monitor.

This confidential document is the property of Abbott and shall not be reproduced, distributed, disclosed or used without the express written consent of Abbott

Clinical Investigation Plan

Any subject enrolled into the clinical investigation who is later found not to meet all eligibility criteria, will be evaluated by the study team. If the deviation is found to violate the scientific integrity of the study or unduly influence the study aims, the subject will be withdrawn from the study. Otherwise, the subject will continue in the study and be included in the analysis population.

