6.5.2 Trial Period

Subjects randomized to receive spinal cord stimulation will first undergo a trial of the therapy. The trial period implementation should start no more than [REDACTED] days after the Baseline visit and should last at least 4 days. Only percutaneous leads may be used for the trial procedure. "On the table" trials and the use of paddle leads for the trial procedure are not allowed.

The following data will be recorded at trial implementation:

- Trial system details
- Device programming
- Device- and/or procedure related adverse events (if applicable)
- All serious adverse events (if applicable)
- Withdrawal (if applicable)

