2.0 ANALYSIS CONSIDERATIONS

2.1 Analysis Populations

The analysis populations include:

1. Intention-to-Treat (ITT) Population: includes all randomized subjects. Subjects will be analyzed according to the treatment group they are randomized to. The ITT population will be used as the primary analysis population for the primary endpoint.
2. Modified Intention-to-Treat (mITT) Population: includes all randomized subjects except for those who are randomized to the SCS group who fail the trial period, do not receive a permanent system implant. Subjects will be analyzed according to the treatment group they are randomized to.
3. Per-Treatment Evaluable (PTE) Population: includes all subjects in the mITT population who either receive permanent implant or receive CMM. Subjects will be analyzed according to the actual treatment received. The PTE population will be used as the primary analysis population for the study except the primary endpoint analysis.

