3.5 Descriptive Endpoints or Additional Data

3.5.1 Descriptive Endpoints

The descriptive endpoints will be analyzed in a PTE fashion. Subjects will be analyzed at each visit by the treatments they received. For example, for NRS, there will be a summary at each visit by the treatments received.

Descriptive endpoints include:

- Proportion of patients who elect to cross-over after the primary endpoint
- Change from baseline at each time point on the following:
 - ODI
 - NRS
 - PROMIS-29 questionnaire
 - Pain Catastrophizing Scale (PCS)
 - Pain-condition related medication usage
 - Exercise frequency
- Healthcare resource utilization
- Device programming and usage
- Patient satisfaction with therapy
- Patient Global Impression of Change (PGIC)
- Serious device-related adverse events

Responder analysis:

- Proportion of subjects with $\geq 30\%$ decrease on NRS
- Proportion of subjects with $\geq 50\%$ decrease on NRS
- Proportion of subjects with $\geq 13\%$ -point improvement, at least one category improvement or score $\leq 20\%$ on ODI
- Proportion of subjects within 1 SD of population norm or reach MCID on PROMIS-29 domains
 1. For the within 1 SD of population norm component:
 - Lower scores are better for negatively worded domains, like anxiety
 - Responder: needs a T-score of ≤ 60
 - Higher scores are better for positively worded domains, like physical function
 - Responder: needs a T-score of ≥ 40
 2. For the MCID component
 - MCIDs will be based on literature
- Proportion of subjects that are either clinically catastrophizing on PCS at baseline (PCS score ≥ 30) and report a score of < 30 at follow up or report a 40% decrease in score at follow-up compared to baseline.

Statistical Analysis Plan

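### The SAP divides device-related adverse events by all enrolled subjects, and its one by-treatment safety output omits SCS subjects who failed the stimulation trial

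*SAP*

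**What the plan says.** SAP 3.2 sets the population for adverse events: "All subjects who completed their enrollments will be included in the analyses". The output is event counts, percentages of subjects with events, and "event rates by subject year for all subjects and by the relatedness (including COVID related) of events". No breakdown by arm, treatment received or lead exposure is given.

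Enrolment is defined in protocol 5.4: "A patient is considered enrolled in the clinical investigation from the moment the patient provides written informed consent", with eligibility and the medical monitor's confirmation also required. Under protocol 6.3 randomisation comes after enrolment.

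SAP 3.5.1 lists "Serious device-related adverse events" as a descriptive endpoint, and for that list it says: "The descriptive endpoints will be analyzed in a PTE fashion. Subjects will be analyzed at each visit by the treatments they received".

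SAP 2.1 defines three populations: ITT, mITT and PTE. The mITT set "includes all randomized subjects except for those who are randomized to the SCS group who fail the trial period" and get no permanent system. PTE is the part of mITT that receives a permanent implant or CMM. No safety or device-exposed set is defined.

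Protocol 6.5.2 requires every subject randomised to SCS to start with a trial of at least 4 days: "Only percutaneous leads may be used for the trial procedure". Device- and procedure-related events and all serious events are recorded at trial implementation and again at the end of the trial (6.5.3).

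**The concern.** A subject with no lead cannot have a device- or procedure-related event. Until crossover, CMM subjects therefore add to the denominator and the subject-years for these events but never to the numerator. Sorting events by relatedness changes which events are counted and leaves the denominator as it was.

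The other safety output errs in the opposite direction. Trial failures had leads placed and are followed for events during the trial, but PTE excludes them. Any serious device-related event they had is absent from the only table that separates treatments. These subjects bore the procedural risk without receiving an implant.

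The comparator involves no implant, so a reader weighing benefit against harm will want the event risk among people who had a lead procedure, and serious events by arm. The SAP states neither. Site staff, subjects and some sponsor staff know the assignment (SAP 1.6), so it is better to fix the denominator in the SAP now than to choose it when the tables are programmed.

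**Working it through.** The documents give no safety figure to reproduce. The check uses the planned size and allocation, and then compares the population definitions.

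**Inputs**
- Phase I 200 subjects, up to 270 with Phase II; allocation 3:2 (SAP 1.3, 2.4).
- SCS: 200 × 0.6 = 120, or 270 × 0.6 = 162. CMM: 80 or 108.
- Assumption: every SCS subject has trial leads placed, and everyone enrolled is randomised.

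**Dilution before crossover**

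Factor = exposed subjects / subjects in the table.
- Phase I: 120/200 = 0.60.
- Full size: 162/270 = 0.60.
- Example: 12 affected subjects are 12/120 = 10.0% of those exposed but are tabulated as 12/200 = 6.0%.

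Subjects enrolled but not randomised, or SCS subjects who never start a trial, would lower the factor further. The subject-year denominator likewise contains all CMM time, and also SCS time before the first lead procedure.

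**Dilution with crossover**

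The documents do not state the share c of CMM subjects who cross over and receive leads. For Phase I the factor is (120 + 80c)/200:

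| Assumed c | Exposed | Factor |
|---|---|---|
| 0 | 120 | 0.60 |
| 0.25 | 140 | 0.70 |
| 0.50 | 160 | 0.80 |
| 0.75 | 180 | 0.90 |

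**Who each output covers**

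| Subject | Had leads | SAP 3.2 table | PTE table (SAP 3.5.1) |
|---|---|---|---|
| SCS, implanted | Yes | Included | Included, by treatment |
| SCS, trial failure | Yes | Included, pooled | Excluded |
| CMM, before or without crossover | No | Included, pooled | Included, by treatment |

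Neither denominator equals the lead-exposed group. Trial failures' events appear only in the pooled SAP 3.2 counts.

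**Size of the PTE omission**

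No trial-failure rate is stated. If 5% to 30% of 120 SCS subjects had leads but no implant (assumed range), 6 to 36 exposed subjects are left out. At an assumed 10% event risk in them, 0.6 to 3.6 affected subjects would be missing; a lower risk scales this down in proportion.

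**The case against.** Several points on the other side are sound.

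- No event disappears. SAP 3.2 includes everyone enrolled and reports event counts by relatedness, so trial failures' events are counted. A reader who also knew how many subjects were trialled and how many were affected could recompute the percentage. This stands; the fault lies in the percentages and rates.
- Some by-treatment safety reporting is planned. Protocol 8.2.3 summarises descriptive endpoints within each treatment group, and PTE gives serious device-related harm among implanted subjects. This stands too, so it would be too strong to say that the plan reports no harm among exposed subjects. What is missing is the whole lead-exposed group.
- The PTE wording in SAP 3.5.1 could be read loosely as analysis by treatment received. Even so, trial failures have no category, because PTE recognises only a permanent implant or CMM.
- The protocol's own list of analysis populations (8.1) is blacked out, so the point can be made only about the SAP.

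Two stronger readings are tempting but unsupported. A reader might infer that serious events cannot be compared between arms. In fact all serious events are reportable in both arms (protocol 7.3.1) and assignment is known, so the comparison is unplanned, not impossible. A reader might also set the 90 SCS subjects expected after attrition (200 × 0.6 × 0.75) against the roughly 80 in PTE in SAP 2.4, and conclude that 10/90 = 11% of exposed subjects are dropped. The SAP does not say that this gap consists of trial failures. Both numbers are approximate planning counts for 6-month analyses, whereas PTE has no 6-month data requirement and adverse event reporting starts at enrolment.

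**Conclusion.** The point holds for the denominators. Followed as written, SAP 3.2 gives device- and procedure-related percentages at about 0.60 of their value among exposed subjects before crossover. This assumes that all SCS subjects are trialled and that all enrolled subjects are randomised. Over the whole study the factor lies closer to 1, depending on a crossover share that the documents do not give. Separately, SAP 3.5.1 leaves trial failures out of the only by-treatment safety output, and no by-arm summary of all serious events is stated. The number of trial failures is unknown.

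This should be fixed before the safety tables are programmed. It is not critical to the trial's main conclusion, because the primary test, the secondary hierarchy and the success criterion do not depend on these tables.

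**What to change.** 1. In SAP 2.1, add a device-exposed safety set: every subject in whom trial or permanent lead placement was attempted, including trial failures. CMM subjects who cross over enter at their first documented lead procedure.
2. In SAP 3.2, report device- and procedure-related event percentages and rates on that set, with exposure time counted from that procedure. Show all serious events by randomised arm up to the 6-month visit. The pooled all-enrolled summary can stay alongside.
3. In SAP 3.5.1, take serious device-related events out of the PTE rule and report them on the safety set.

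The cost is SAP wording and table shells. For subjects randomised to SCS, the trial and implant details and the events are already recorded. Failed crossover trials are less certain: protocol 6.6.4 places crossover trials within standard of care and describes continued study follow-up upon permanent implant. They can be included only as far as their data are collected, and the SAP should say so. The downside for the sponsor is a less favourable reported device-related percentage. Power and the primary analysis do not change.
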